- **Study design:** This is a retrospective observational study utilizing de-identified data from Japan Hospital administrative claims data (Medical Data Vision [MDV]).
- **Population:** The study population will include all adults aged 18 years or older with an MM diagnosis who initiate elranatamab on or after March 26, 2024 (PMDA Elrexfio approval date). Patients with evidence of clinical trial participation will be excluded.
- **Variables:** The following variables will be summarized and reported:

Exposure of interest:

Exposure is defined as at least one record of a hospital claim for elranatamab on or after March 26, 2024. All patients included in the study will be considered exposed. Analyses of outcomes during the SUD period will also be stratified based on types of elranatamab exposure during that time (i.e., complete and timely SUD, complete but not timely SUD, alternative SUD). Clinical data will be collected from MDV hospital data.

Study outcomes:

Study endpoints include: elranatamab timing and dosing (i.e., types of doses, time between doses, relative administration intensity), HCRU and costs (i.e., IP/OP/ED claims and associated costs, degree of nursing), other MM treatment post elranatamab administration (i.e., PIs, SCT, supportive therapy), known adverse events (i.e., CRS events occurrence, frequency and associated length of stay, time from index to CRS event), infection (i.e., infection occurrence, time from index to infection, antibiotics), and supportive medication (i.e., IVIG, acetaminophen, dexamethasone).

Covariates:

Covariates will include baseline demographics (i.e., age, sex, weight etc.), and baseline clinical characteristics (i.e., comorbidities and treatment history).

- **Data sources:** The MDV database is a comprehensive resource containing administrative data from over 540 hospitals in Japan. This dataset includes information on demographics, mortality, labs, IP, OP, ED claims, treatments, procedures and costs of approximately 50 million patients. MDV is an aggregated, de-identified dataset where no patient can be individually identified and therefore no patient consent is required.
- **Study size:** This is a retrospective descriptive study with no a priori hypotheses; therefore, sample size calculations are not applicable. As of February 2025, MDV included 128 patients that had at least one hospital claim for an elranatamab administration.

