9.3.1 Exposure Groups and Assessment Periods

[Table 1](#) outlines the variables to define exposure groups that will be used to identify patients and stratify analyses.

Table 1. Variables for Exposure

Variable	Role	Data Source	Operational Definition	
			Definition	Assessment Period(s)
Study population	Exposure	MDV	All patients with MM who have a hospital claim for elranatamab after March 26, 2024, and who meet the inclusion and exclusion criteria outlined in Sections 9.2.1 and 9.2.2.	Index date
SUD Exposure Group	Exposure	MDV	
Group A: Complete and timely SUD period
 
Patients in the study population with two 44mg/1.1mL vials (second 44mg/1.1mL vial is received 1 to 7 days after the first) and one subsequent 76mg/1.9mL vial between 1 to 7 days after second 44mg/1.1mL vial
 
Group B: Complete but not timely SUD period
 
Patients in the study population with two 44mg/1.1mL vials and one subsequent 76mg/1.9mL vial after the second 44mg/1.1mL vial, with one or both intervals between doses ranging from 8 to 14 days.
 
Group C: Alternative SUD period
 
 • Only one 44mg/1.1mL vial: patients in the study population with only one 44mg/1.1mL vial prior to receiving a 76mg/1.9mL vial • More than two 44mg/1.1mL vials: patients in the study population with more than 	SUD period

090177e1a4a71ff1\Approved\Approved On: 05-Nov-2025 14:15 (GMT)

Variable	Role	Data Source	Operational Definition	
			Definition	Assessment Period(s)
			
two 44mg/1.1mL vials prior to receiving a 76mg/1.9mL vial
 
 Extremely untimely: patients in the study population with more than 14 days between the first and second 44mg/1.1mL vial or between the second 44mg/1.1mL vial and the first 76mg/1.9mL vial 
Note that patients who received only 44mg/1.1mL vials or only 76mg/1.9mL vials are not classified under any SUD exposure group but will remain part of the study population.
	

Figure 2 illustrates possible elranatamab administration scenarios for each SUD group. These examples are not exhaustive and do not represent all potential administration schedules.

090177e1a4a71ff1\Approved\Approved On: 05-Nov-2025 14:15 (GMT)

Figure 2. SUD Periods Administration Schedule

[figure not shown]

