Table 2 summarizes the patient exposure groups and assessment periods during which endpoints for each study objective will be measured. Patients will be included in the follow-up sub-period analyses if they have at least one claim for elranatamab or if the end date of their follow-up period falls within the sub-period's time frame.

Table 2. Patient Exposure Groups Stratification and Assessment Period for Study Objectives

Study Objective	Assessment period	Patient Exposure Groups
Objective 1 – Patient Characteristics	Baseline period	Study population
	Index date	Group A, Group A+B, Group C
Objective 2 – Treatment administration, dosing and timing	SUD period 
 Overall (Between first 44mg/1.1mL vial – first 76mg/1.9mL vial) Between first 44mg/1.1mL vial – second 44mg/1.1mL vial Between second 44mg/1.1mL vial – first 76mg/1.9mL vial 	Group A, Group A+B, Group C
	Follow-up period 
 Index date 	Study population

090177e1a4a71ff1\Approved\Approved On: 05-Nov-2025 14:15 (GMT)

Study Objective	Assessment period	Patient Exposure Groups
	
 • Index date (day 1) to day 8 • Day 9 to day 168 • Day 169 to end of follow-up period • Overall (day 1 to end of follow-up period) 	
Objective 3 – HCRU and costs	HCRU baseline assessment period	Study population
	SUD period 
 • Overall (Between first 44mg/1.1mL vial – first 76mg/1.9mL vial) • Between first 44mg/1.1mL vial – second 44mg/1.1mL vial • Between second 44mg/1.1mL vial – first 76mg/1.9mL vial 	Group A, Group A+B, Group C
	Follow-up period 
 • Index date • Index date (day 1) to day 8 • Day 9 to day 168 • Day 169 to end of follow-up period • Overall (day 1 to end of follow-up period) 	Study population
Objective 4 – Other MM treatments including supportive therapy	Follow-up period 
 • Index date • Index date (day 1) to day 8 • Day 9 to day 168 • Day 169 to end of follow-up period • Overall (day 1 to end of follow-up period) 	Study population
Objective 5 – Known adverse events	CRS/ICANS follow-up assessment period (CRS/ICANS events)	Group A, Group A+B, Group C
	SUD period (Cytopenia events) 
 • Overall (Between first 44mg/1.1mL vial – first 76mg/1.9mL vial) 	Group A, Group A+B, Group C

090177e1a4a71ff1Approved\Approved On: 05-Nov-2025 14:15 (GMT)

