Antifungals	Baseline characteristics	MDV	Health claim code for antifungal medications (Yes/No)	14 days prior index date 365 days prior index date

Abbreviations: ADL: Activity of Daily Living; CAR-T: chimeric antigen receptor T-cell therapy; CCI: Charlson Comorbidity Index; cm: centimeter; IMiDs: immunomodulatory agents; IP: inpatient; IVIG: intravenous immunoglobulin; lb: pound; OP: outpatient; PI: proteasome inhibitors; SCT: stem cell transplant.

Table 4. Variables for Outcomes (Objective 2 - Treatment Administration, Dosing and Timing)

Variable	Role	Data Source	Operational Definition	
			Definition	Assessment Period(s)
44mg/1.1mL vial and 76mg/1.9mL vial [Summary statistic]	Outcome	MDV	Number of health claims for elranatamab per patient in the following categories: 
 ● 44mg/1.1mL vial ● 76mg/1.9mL vial 	SUD period

090177e1a4a71ff1\Approved\Approved On: 05-Nov-2025 14:15 (GMT)

Variable	Role	Data Source	Operational Definition	
			Definition	Assessment Period(s)
			Total number of health claims for elranatamab in the following categories: 
 • 44mg/1.1mL vial • 76mg/1.9mL vial 	Follow-up period
Time between first and second 44mg/1.1mL vials	Outcome	MDV	Days between claims for the first and second 44mg/1.1mL vial of elranatamab (continuous) Patients with <2 44mg/1.1mL vials are not included.	SUD period
Time between first 44mg/1.1mL vial and first 76mg/1.9mL vial	Outcome	MDV	Days between claims for the first 44mg/1.1mL vial and first 76mg/1.9mL vial of elranatamab (continuous)	SUD period
Time between second 44mg/1.1mL vial and first 76mg/1.9mL vial	Outcome	MDV	Days between claims for the second 44mg/1.1mL vial and first 76mg/1.9mL vial of elranatamab (continuous) Patients with <2 44mg/1.1mL vials are not included	SUD period
Time between elranatamab claims, patient level	Outcome	MDV	For patients with at least 2 elranatamab claims, the mean number of days between claims for elranatamab per patient will be reported	Follow-up period
Time between elranatamab claims, claim level	Outcome	MDV	For patients with at least 2 elranatamab claims, the mean number of days between claims for elranatamab will be reported alongside the number of intervals	Follow-up period

090177e1a4a71ff1\Approved\Approved On: 05-Nov-2025 14:15 (GMT)

Variable	Role	Data Source	Operational Definition	
			Definition	Assessment Period(s)
			between administrations in a given time period.	

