9.7. Data Analysis

All analysis will be descriptive in nature and no formal statistical comparisons will be performed between groups. All characteristics and endpoints will be reported separately for each assessment period and patient exposure groups of interest as defined in [Table 2. Patient Exposure Groups Stratification and Assessment Period for Study Objectives](#).

Raw data transferred by MDV will be reviewed for completeness, consistency and plausibility. Records with missing or implausible values (e.g., negative age, invalid dates) will be flagged and addressed according to predefined rules in the SAP. Duplicate records will be identified and removed. Variables will be derived and categorized as needed for analysis. Diagnosis and procedure codes will be mapped to standardized categories using the International Classification of Diseases, 10th revision (ICD-10) and Healthcare Common Procedure Coding System (HCPCS) classification systems. Missing data will be reported, and no imputation will be performed unless otherwise specified in the SAP.

Detailed methodology for summary and statistical analyses of data collected in this study will be documented in a SAP, which will be dated, filed, and maintained by the sponsor. The SAP may modify the plans outlined in the protocol; any major modifications of primary endpoint definitions or their analyses would be reflected in a protocol amendment.

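### Step-up timing and vial counts under primary Objective 2 are reported only within groups defined by those same intervals and counts, and no pooled result is specified

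*Protocol*

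**What the plan says.** Objective 2 (Section 8) is primary. It describes elranatamab utilization, including timing, administration and dosing, over follow-up and the SUD period.

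Table 4 (Section 1.1.2) gives the SUD-period outcomes. The first interval is "Days between claims for the first and second 44mg/1.1mL vial of elranatamab (continuous"). The others are days from first 44mg to first 76mg vial, days from second 44mg to first 76mg vial, and vials per patient by size.

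Table 2 (Section 9.3.1) assigns the Objective 2 SUD-period rows to "Group A, Group A+B, Group C". The word overall in those rows means the whole SUD window, not all patients. Section 9.7 makes Table 2 the reporting rule: "All characteristics and endpoints will be reported separately for each assessment period and patient exposure groups of interest as defined in" Table 2.

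Table 1 (Section 9.3.1) defines the groups:
- Group A has two 44mg vials, where the "second 44mg/1.1mL vial is received 1 to 7 days after the first", and a 76mg vial 1 to 7 days after that.
- Group B has the same vials "with one or both intervals between doses ranging from 8 to 14 days".
- Group C has only one 44mg vial, or more than two, or is extremely untimely, for example "patients in the study population with more than 14 days between the first and second 44mg/1.1mL vial".
- Patients with only 44mg or only 76mg vials belong to no group but stay in the study population.

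The abstract says: "Analyses of outcomes during the SUD period will also be stratified based on types of elranatamab exposure during that time".

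**The concern.** A summary of a variable within groups cut on that variable partly reports the cut-points. In Group A the maximum gap cannot exceed 7 days, whatever happens in practice. The Group A median and IQR must also lie between 1 and 7, which could be read as good adherence to schedule when it follows from the definition. The strata are sound for outcomes that do not define them, such as resource use or cytokine release syndrome. For the intervals and the 44mg count themselves they need a pooled result beside them, and Table 2 lists none. At stake is the direct answer to a primary descriptive question: the typical length and spread of step-up dosing among patients who go through it.

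**Working it through.** The protocol states no figure to reproduce for this point. The check has three parts.

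**1. What each group allows.** I enumerated whole-day gap pairs (1 to 60 days each) for patients with two 44mg vials, under the Table 1 rules.

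| Group | Each gap (days) | First 44mg to first 76mg (days) | 44mg count |
|---|---|---|---|
| A | 1–7 | 2–14 | always 2, SD 0 |
| A+B | 1–14 | 2–28 | always 2, SD 0 |
| C, extremely untimely | at least one gap over 14 | 16 or more | 2 |
| C, one or more than two 44mg vials | no limit | no limit | 1, or 3 and more |

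The 76mg count is 1 in every group, because the SUD period ends at the first 76mg vial (Section 9.2). The 14-day cap follows Table 1. Table 12 in Annex 2 places a gap of exactly 14 days in both Group B and the extremely untimely part of Group C. A pooled result would not depend on how that is resolved.

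**2. What can be recovered.** A+B and C are disjoint and together hold every classified patient. Section 9.7.1 requires mean, SD, median, IQR, minimum and maximum. With N the number of patients contributing to the variable:
- Pooled mean = (N_AB × mean_AB + N_C × mean_C) / (N_AB + N_C). The pooled SD follows from the same Ns, means and SDs.
- Pooled minimum and maximum are the smaller minimum and the larger maximum.
- Pooled median and quartiles are not functions of the group summaries.

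A check of the mean on simulated data (median gap 5 days, all patients with two 44mg vials, 82.3% in A+B and 17.7% in C): 0.823 × 5.33 + 0.177 × 14.30 = 4.39 + 2.53 = 6.92, against 6.91 computed directly. In practice the rebuilt values carry the one-decimal rounding of Section 9.7.1.

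**3. Size, as an illustration only.** The protocol gives no distribution of gaps, so the inputs here are assumptions: independent log-normal gaps with log-SD 0.8, rounded to whole days (minimum 1), and 15% of patients with one or three 44mg vials. The share of gaps over 7 days is 1 − Φ(ln(7.5/median)/0.8), where 7.5 allows for rounding. For medians of 3, 5 and 8 days this gives about 13%, 31% and 53%.

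Mean (median) days from first to second 44mg vial:

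| Assumed median gap | A | A+B | C | A+B+C |
|---|---|---|---|---|
| 3 days | 3.0 (3) | 3.7 (3) | 6.9 (4) | 4.1 (3) |
| 5 days | 3.8 (4) | 5.3 (5) | 11.8 (8) | 6.9 (5) |
| 8 days | 4.4 (4) | 6.8 (6) | 16.1 (15) | 11.0 (8) |

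From the two-decimal means, the A and A+B shortfalls against the pooled mean are:
- median 3: (4.14 − 3.01)/4.14 = 27% and (4.14 − 3.73)/4.14 = 10%
- median 5: (6.89 − 3.82)/6.89 = 45% and (6.89 − 5.33)/6.89 = 23%
- median 8: (11.03 − 4.44)/11.03 = 60% and (11.03 − 6.81)/11.03 = 38%

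The A+B median equals the pooled median in the first two cases and is 2 days lower in the third. With a median of 4 days and only 10% of gaps over 7 days, the mean shortfalls drop to 13% (A) and 1% (A+B). At 20% they are 33% and 13%, and the A+B and pooled medians agree: 4 days for the first gap and 9 days for first 44mg to first 76mg.

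**The case against.** The best defence is that little is lost. Mean, SD and range can be rebuilt, group sizes show how many patients fall into each timeliness class, and the A+B median may equal the pooled one when late gaps are uncommon. The abstract's wording suggests that an unstratified result was intended, and a total column is the kind of detail that a statistical analysis plan often adds. Section 9.7 allows that plan to modify the protocol.

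Much of this stands, and it limits the point. A reader might infer that the overall spread of step-up timing cannot be recovered at all. That is wrong: only the median and IQR are lost. A reader might also infer that all three groups are truncated on gap length. In Group C this holds only for the extremely untimely part. The rest is selected on vial count, and Table 12 sets no time requirement for it.

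Two parts of the defence do not stand. First, the reporting groups are not left open. Table 2 names them, uses the study population in other rows, and is made the rule by Section 9.7. Second, the study-population follow-up rows do not fill the gap. They give days between any elranatamab claims, which over the whole follow-up mixes step-up with later dosing. Within days 1 to 8, two claims can be at most 7 days apart.

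**Conclusion.** The point holds as a shortcoming in reporting that is easily mended. Under Tables 1, 2 and 4, the A and A+B summaries of the step-up intervals are capped at 7 and 14 days and the vial count is constant in both. No pooled median or IQR would be available for a primary objective. These statements follow from the definitions and need no assumption. Table 2 also sits awkwardly with the abstract.

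The size is not known. In the illustrations the A+B mean falls short of the pooled mean by between 1% and 38%, depending wholly on the assumed share and length of late gaps. Larger shortfalls can be produced. Holding the median at 4 days with 30% of gaps over 7 days gives 64% in A and 47% in A+B, but that scenario generates single gaps above 1,000 days and should carry no weight. The documents do not support saying that step-up timing goes undescribed, or that any stated result would be wrong.

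**What to change.** In Table 2, Objective 2, SUD period, add a pooled column of all patients with an evaluable SUD period (Groups A+B+C) for the Table 4 SUD variables. Report the Section 9.7.1 statistics and name this column as the main description of step-up timing. Use A+B+C and not the whole study population, because patients with only 44mg or only 76mg vials have no complete SUD period as Section 9.2 defines it.

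Report the number and percentage of patients in each SUD group and in the unclassified only-44mg and only-76mg sets. Keep A, A+B and C as strata alongside, since they still show, for example, how late the Group C patients are. Align the abstract and Table 2.

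The cost is one extra table column and a wording change. No new data are needed.

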1.1.2. Covariates and Outcomes

Table 3 to Table 9 includes definitions and assessment periods for all study variables and that will be used to address the study objectives. Variables for which summary statistics across individuals are produced are identified in the table below. If applicable, the frequency and percentage of patients with missing data for each variable will be described.

Table 3. Variables for Baseline Characteristics (Objective 1 – Patient Characteristics)

090177e1a4a71ff1\Approved\Approved On: 05-Nov-2025 14:15 (GMT)

Variable	Role	Data Source	Operational Definition	
			Definition	Assessment Period
Age	Baseline characteristics	MDV	
Age at index date, in years.
 
Age will be reported as a continuous variable as well as a categorical variable for the following age groups:
 
 • <65 • 65-69 • 70-74 • ≥75 	Index date
Sex	Baseline characteristics	MDV	
Sex, N (%)
 
 • Male • Female 	Index date
Weight	Baseline characteristics Sub-group identifier	MDV	Weight assessment before and closest to the index date, lb	Baseline period
Height	Baseline characteristics	MDV	Height assessment before and closest to the index date, cm	Baseline period
Smoking index	Baseline characteristics	MDV	
Smoking index assessment before and closest to the index date
 
Smoking index = Number of cigarettes smoked * years of smoking
	Baseline period
Care setting	Baseline characteristics	MDV	
Care setting for the first elranatamab administration
 
 • Inpatient (IP) • Outpatient (OP) 	Index date

090177e1a4a71ff1\Approved\Approved On: 05-Nov-2025 14:15 (GMT)

Variable	Role	Data Source	Operational Definition	
			Definition	Assessment Period
Hospital scale	Baseline characteristics	MDV	Number of hospital beds in hospital admitted at index date (categorical) 
 • ≤199 beds • 200-499 beds • ≥500 beds 	Index date
Hospital category	Baseline characteristics	MDV	Hospital category at index date (categorical) 
 • University hospital • Public hospital (local) • Public hospital (National) • Private hospital 	Index date
CCI 
 • Myocardial infarction • Congestive heart failure • Peripheral vascular failure • Cerebrovascular disease • Dementia • Chronic pulmonary disease • Rheumatic disease • Peptic ulcer disease • Mild liver disease • Severe liver disease • Diabetes w/o chronic complication • Diabetes with chronic complication • Mild renal disease 	Baseline characteristics	MDV	Health claim code for comorbidities. CCI score using Glasheen algorithm (13) will be reported (continuous and categorical): 
 • 0 to 1 • 2 to 5 • 6 to 9 • ≥ 10 Health claim code for each comorbidity will be reported.	180 days prior to index date 365 days prior to index date

090177e1a4a71ff1\Approved\Approved On: 05-Nov-2025 14:15 (GMT)

Variable	Role	Data Source	Operational Definition	
			Definition	Assessment Period

 Severe renal disease Hemiplegia or paraplegia Human immunodeficiency virus AIDS Metastatic solid tumor Malignancy 				
Activities of Daily Living (ADL) score	Baseline characteristics	MDV	ADL Score assessment before and closest to index date (categorical)	Baseline period
Hypercalcemia	Baseline characteristics	MDV	Disease code for hypercalcemia (Yes/No)	Baseline period
Hepatotoxicity	Baseline characteristics	MDV	Disease code for hepatotoxicity (Yes/No)	Baseline period
Renal failure	Baseline characteristics	MDV	Disease code for renal failure (Yes/No)	Baseline period
Amyloidosis	Baseline characteristics	MDV	Disease code for amyloidosis (Yes/No)	Baseline period
Hypertension	Baseline characteristics	MDV	Disease code for hypertension (Yes/No)	Baseline period
Plasmacytoma	Baseline characteristics	MDV	Disease code for plasmacytoma (Yes/No)	Baseline period
Extramedullary disease	Baseline characteristics	MDV	Disease code for extramedullary disease (Yes/No)	Baseline period

090177e1a4a71ff1\Approved\Approved On: 05-Nov-2025 14:15 (GMT)

Variable	Role	Data Source	Operational Definition	
			Definition	Assessment Period
Other hematological malignancies	Baseline characteristics	MDV	Disease code for hematological malignancies other than MM (Yes/No)	Baseline period
Any non-hematological malignancy	Baseline characteristics	MDV	Disease code for non-hematological malignancies (Yes/No)	Baseline period
Plasma cell leukemia	Baseline characteristics	MDV	Disease code for plasma cell leukemia (Yes/No)	Baseline period
Bone lesion	Baseline characteristics	MDV	Disease code for bone lesions (Yes/No)	Baseline period
Peripheral neuropathy	Baseline characteristics	MDV	Disease code for peripheral neuropathy (Yes/No)	Baseline period
Time since MM diagnosis	Baseline characteristics	MDV	Time (in months) from initial MM diagnosis to index date (continuous)	Baseline period
PIs	Baseline characteristics	MDV	Health claim code for bortezomib, carfilzomib, or ixazomib (Yes/No) Health claim code for each PI will also be reported.	Baseline period
IMiDs	Baseline characteristics	MDV	Health claim code for lenalidomide, thalidomide, or pomalidomide (Yes/No) Health claim code for each IMiD will also be reported.	Baseline period
anti-CD38s	Baseline characteristics	MDV	Health claim code for daratumumab, or isatuximab (Yes/No)	Baseline period

090177e1a4a71ff1\Approved\Approved On: 05-Nov-2025 14:15 (GMT)

Variable	Role	Data Source	Operational Definition	
			Definition	Assessment Period
			Health claim code for each anti-CD38 will also be reported.	
Penta-drug exposed	Baseline characteristics	MDV	Health claim code for all of the following therapies (Yes/No): 
 • ≥2 distinct PIs (see generic names above) • ≥2 distinct IMiDs (see generic names above) • ≥1 CD38 mAbs (generic names above) 	Baseline period
Stem-cell transplant (SCT)	Baseline characteristics	MDV	Health claim code for SCT (Yes/No) Health claim code for each SCT type (allogeneic and autologous) will be reported.	Baseline period
CAR-T	Baseline characteristics	MDV	Health claim code for idecabtagene vicleucel or ciltacabtagene autoleucel (Yes/No) Health claim code for each CAR-T will be reported.	Baseline period
Chemotherapies	Baseline characteristics	MDV	Health claim code for chemotherapies (doxorubicin hydrochloride, melphalan, bendamustine, cyclophosphamide, etoposide, or cisplatin) (Yes/No) Health claim code for each chemotherapy will also be reported.	Baseline period
Intravenous immunoglobulin (IVIG)	Baseline characteristics	MDV	Health claim code for IVIG (Yes/No)	Baseline period

090177e1a4a71ff1\Approved\Approved On: 05-Nov-2025 14:15 (GMT)

Variable	Role	Data Source	Operational Definition	
			Definition	Assessment Period
Antibiotics	Baseline characteristics	MDV	Health claim code for antibiotic medications (Yes/No)	14 days prior index date 365 days prior index date
Antivirals	Baseline characteristics	MDV	Health claim code for antiviral medications (Yes/No)	14 days prior index date 365 days prior index date
Antifungals	Baseline characteristics	MDV	Health claim code for antifungal medications (Yes/No)	14 days prior index date 365 days prior index date

Abbreviations: ADL: Activity of Daily Living; CAR-T: chimeric antigen receptor T-cell therapy; CCI: Charlson Comorbidity Index; cm: centimeter; IMiDs: immunomodulatory agents; IP: inpatient; IVIG: intravenous immunoglobulin; lb: pound; OP: outpatient; PI: proteasome inhibitors; SCT: stem cell transplant.

Table 4. Variables for Outcomes (Objective 2 - Treatment Administration, Dosing and Timing)

Variable	Role	Data Source	Operational Definition	
			Definition	Assessment Period(s)
44mg/1.1mL vial and 76mg/1.9mL vial [Summary statistic]	Outcome	MDV	Number of health claims for elranatamab per patient in the following categories: 
 ● 44mg/1.1mL vial ● 76mg/1.9mL vial 	SUD period

090177e1a4a71ff1\Approved\Approved On: 05-Nov-2025 14:15 (GMT)

Variable	Role	Data Source	Operational Definition	
			Definition	Assessment Period(s)
			Total number of health claims for elranatamab in the following categories: 
 • 44mg/1.1mL vial • 76mg/1.9mL vial 	Follow-up period
Time between first and second 44mg/1.1mL vials	Outcome	MDV	Days between claims for the first and second 44mg/1.1mL vial of elranatamab (continuous) Patients with <2 44mg/1.1mL vials are not included.	SUD period
Time between first 44mg/1.1mL vial and first 76mg/1.9mL vial	Outcome	MDV	Days between claims for the first 44mg/1.1mL vial and first 76mg/1.9mL vial of elranatamab (continuous)	SUD period
Time between second 44mg/1.1mL vial and first 76mg/1.9mL vial	Outcome	MDV	Days between claims for the second 44mg/1.1mL vial and first 76mg/1.9mL vial of elranatamab (continuous) Patients with <2 44mg/1.1mL vials are not included	SUD period
Time between elranatamab claims, patient level	Outcome	MDV	For patients with at least 2 elranatamab claims, the mean number of days between claims for elranatamab per patient will be reported	Follow-up period
Time between elranatamab claims, claim level	Outcome	MDV	For patients with at least 2 elranatamab claims, the mean number of days between claims for elranatamab will be reported alongside the number of intervals	Follow-up period

090177e1a4a71ff1\Approved\Approved On: 05-Nov-2025 14:15 (GMT)

Variable	Role	Data Source	Operational Definition	
			Definition	Assessment Period(s)
			between administrations in a given time period.	
Duration of treatment, patient level	Outcome	MDV	Days between first and last treatment administration for elranatamab (continuous)	Follow-up period
Duration of treatment, claim level	Outcome	MDV	Total calendar duration of elranatamb observation in days, and the date of the first observed elrantatamab claim	Follow-up period
Only 44mg/1.1mL vials [Summary statistic]	Outcome	MDV	Number of patients with only 44mg/1.1mL vials during the time period (yes/no)	Follow-up period
Only 76mg/1.9mL vials [Summary statistic]	Outcome	MDV	Number of patients with only 76mg/1.9mL vials during the time period (yes/no)	Follow-up period
Relative Administration Intensity (RAI) [Summary statistic]	Outcome	MDV	Ratio of the elranatamab administrations received divided by the expected number of administrations according to the Japan elranatamab label See Section 9.7.4 for more details	Follow-up period

Abbreviations: mL: millilitre; mg: milligram; RAI: Relative Administration Intensity; SUD: step-up dosing.

Table 5. Variables for Outcomes (Objective 3 – HCRU and Costs)

090177e1a4a71ff1\Approved\Approved On: 05-Nov-2025 14:15 (GMT)

Variable	Role	Data Source	Operational Definition	
			Definition	Assessment Period(s)
IP claim [Summary statistic]	Outcome	MDV	Number of patients with ≥ 1 all-cause IP claim (yes/no)	HCRU baseline period SUD period Follow-up period (overall only)
			Number of all-cause IP claims PPPM. Reported for all patients and for patients with ≥ 1 all-cause IP claim.	HCRU baseline period Follow-up period (overall only)
			Number of all-cause IP claims PPPD. Reported for all patients and for patients with ≥ 1 all-cause IP claim.	SUD period
OP claim [Summary statistic]	Outcome	MDV	Number of patients with ≥ 1 all-cause OP claim (yes/no)	HCRU baseline period SUD period Follow-up period (overall only)
			Number of all-cause OP claims PPPM. Reported for all patients and for patients with ≥ 1 all-cause OP claim.	HCRU baseline period Follow-up period (overall only)
			Number of all-cause OP claims PPPD. Reported for all patients and for patients with ≥ 1 all-cause OP claim.	SUD period

090177e1a4a71ff1\Approved\Approved On: 05-Nov-2025 14:15 (GMT)

Variable	Role	Data Source	Operational Definition	
			Definition	Assessment Period(s)
ED claim [Summary statistic]	Outcome	MDV	Number of patients with ≥ 1 all-cause ED claim (yes/no)	HCRU baseline period SUD period Follow-up period (overall only)
			Number of all-cause ED claims PPPM. Reported for all patients and for patients with ≥ 1 all-cause ED claim.	HCRU baseline period Follow-up period (overall only)
			Number of all-cause ED claims PPPD. Reported for all patients and for patients with ≥ 1 all-cause ED claim.	SUD period
Any HCRU (IP, OP, and ED) claim [Summary statistic]	Outcome	MDV	Number of patients with ≥ 1 all-cause HCRU (IP, OP, and ED) claim (yes/no)	HCRU baseline period SUD period Follow-up period (overall only)
			Number of all-cause HCRU claims PPPM. Reported for all patients and for patients with ≥ 1 all-cause HCRU claim.	HCRU baseline period Follow-up period (overall only)
			Number of all-cause HCRU claims PPPD.	SUD period

090177e1a4a71ff1\Approved\Approved On: 05-Nov-2025 14:15 (GMT)

Variable	Role	Data Source	Operational Definition	
			Definition	Assessment Period(s)
			Reported for all patients and for patients with ≥ 1 all-cause HCRU claim.	
Cost of IP claims [Summary statistic]	Outcome	MDV	Total cost of IP claims PPPM	HCRU baseline period Follow-up period (overall only)
			Total cost of IP claims PPPD	SUD period
Cost of OP claims [Summary statistic]	Outcome	MDV	Total cost of OP claims PPPM	HCRU baseline period Follow-up period (overall only)
			Total cost of OP claims PPPD	SUD period
Cost of ED claims [Summary statistic]	Outcome	MDV	Total cost of ED claims PPPM	HCRU baseline period Follow-up period (overall only)
			Total cost of ED claims PPPD	SUD period
Cost of HCRU claims [Summary statistic]	Outcome	MDV	Total cost of all-cause HCRU claims PPPM	HCRU baseline period Follow-up period (overall only)

090177e1a4a71ff1\Approved\Approved On: 05-Nov-2025 14:15 (GMT)

Variable	Role	Data Source	Operational Definition	
			Definition	Assessment Period(s)
			Total cost of all-cause HCRU claims PPPD	SUD period
Total duration of all-cause IP claims	Outcome	MDV	The total time in days of IP stays among patients who have at least 1 IP stay (continuous).	HCRU baseline period Follow-up period
Duration of all-cause IP claims	Outcome	MDV	Days of IP stays among patients who have at least 1 IP stay PPPM	HCRU baseline period Follow-up period
Department visits claims [Summary statistic]	Outcome	MDV	Number of patients with top 5 most common department visits claims (yes/no) Note that the top 5 will not be established a priori, but rather will be determined based on the data and sample	HCRU baseline period SUD period Follow-up period (overall only)
			Number of top 5 department visits claims PPPM Note that the top 5 will not be established a priori, but rather will be determined based on the data and sample	HCRU baseline period Follow-up period (overall only)
			Number of top 5 department visits claims PPPD Note that the top 5 will not be established a priori, but rather will be determined based on the data and sample	SUD period

090177e1a4a71ff1\Approved\Approved On: 05-Nov-2025 14:15 (GMT)

Variable	Role	Data Source	Operational Definition	
			Definition	Assessment Period(s)
Degree of nursing	Outcome	MDV	Highest degree of nursing recorded (categorical), N (%) For the following categories: No support, Support level 1, Support level 2, Care level 1, Care level 2, Care level 3, Care level 4, Care level 5, Is applying, Unknown	HCRU baseline period SUD period Follow-up period (overall only)

Abbreviations: ED: emergency department; HCRU: healthcare resource utilization; IP: inpatient; OP: outpatient; PPPD: per patient per day; PPPM: per patient per month; SUD: step-up dosing.

Table 6. Variables for Outcomes (Objective 4 - Other MM treatments including supportive therapy)

Variable	Role	Data Source	Operational Definition	
			Definition	Assessment Period(s)
PIs	Outcome	MDV	Health claim code for bortezomib, carfilzomib, or ixazomib (Yes/No) Health claim code for each PI will also be reported.	Follow-up period
IMiDs	Outcome	MDV	Health claim code for lenalidomide, thalidomide, or pomalidomide (Yes/No) Health claim code for each IMiD will also be reported.	Follow-up period
anti-CD38s	Outcome	MDV	Health claim code for daratumumab, or isatuximab (Yes/No)	Follow-up period

Variable	Role	Data Source	Operational Definition	
			Definition	Assessment Period(s)
			Health claim code for each anti-CD38 will also be reported.	
SCT	Outcome	MDV	Health claim code for SCT (Yes/No) Health claim code for each SCT (allogeneic and autologous) will be reported.	Follow-up period
CAR-T	Outcome	MDV	Health claim code for idecabtagene vicleucel or ciltacabtagene autoleucel (Yes/No) Health claim code for each CAR-T will be reported.	Follow-up period
Chemotherapies	Outcome	MDV	Health claim code for chemotherapies (doxorubicin hydrochloride, melphalan, bendamustine, cyclophosphamide, etoposide, or cisplatin) (Yes/No) Health claim code for each chemotherapy will also be reported.	Follow-up period
IVIG	Outcome	MDV	Health claim code for IVIG (Yes/No)	Follow-up period

Abbreviations: CAR-T: chimeric antigen receptor T-cell therapy; IMiDs: immunomodulatory agents; IVIG: intravenous immunoglobulin; PI: proteasome inhibitors; SCT: stem cell transplant;

Table 7. Variables for Outcomes (Objective 5 – Known Adverse Events)

Variable	Role	Data Source	Operational Definition	
			Definition	Assessment Period(s)
CRS events ¹	Outcome	MDV	Disease code for CRS (Yes/No)	CRS/ICANS follow-up

Variable	Role	Data Source	Operational Definition	
			Definition	Assessment Period(s)
			(14) Incidence and prevalence will be reported, see Section 9.7.2 for additional details.	assessment period
Frequency of CRS events	Outcome	MDV	Total number of CRS events during the time period per patient (categorical) 
 • 1 CRS event • 2 CRS events • 3 or more CRS events 	CRS/ICANS follow-up assessment period
CRS Concomitant medications	Outcome	MDV	Disease code for concomitant medications (i.e., IV hydration) received on the same day as the CRS event (Yes/No)	CRS/ICANS follow-up assessment period
Length of stay for CRS events	Outcome	MDV	The total time in days of the CRS hospital stays among patients who have at least 1 CRS event (continuous).	CRS/ICANS follow-up assessment period
Days from index to first CRS event	Outcome	MDV	Time in days from index date to first CRS event (continuous)	CRS/ICANS follow-up assessment period
ICANS events ¹	Outcome	MDV	Disease code for ICANS (Yes/No) Incidence and prevalence will be reported, see Section 9.7.2 for additional details.	CRS/ICANS follow-up assessment period
Frequency of ICANS events	Outcome	MDV	Total number of ICANS events during the time period per patient (categorical) 
 • 1 ICANS event • 2 ICANS events 	CRS/ICANS follow-up assessment period

090177e1a4a71ff1\Approved\Approved On: 05-Nov-2025 14:15 (GMT)

Variable	Role	Data Source	Operational Definition	
			Definition	Assessment Period(s)
			
 3 or more ICANS events 	
ICANS Concomitant medications	Outcome	MDV	Disease code for concomitant medications (i.e., IV hydration) received on the same day as the ICANS event (Yes/No)	CRS/ICANS follow-up assessment period
Length of stay for ICANS events	Outcome	MDV	The total time in days of the ICANS hospital stays among patients who have at least an IP stay with ≥ 1 ICANS event (continuous).	CRS/ICANS follow-up assessment period
